Subjects: In order to be eligible for this study, subjects must: 1) be African American (based on self-identification); 2) smoke primarily menthol cigarettes (greater than 80% of products used are menthol); 3) be between the ages of 18 and 64; 4) Smoke on average at least 5 cigarettes per day for a period longer than 1 year; and 5) agree to abstain from menthol cigarettes for an 8 week period. Subjects will be excluded if they have: 1) a current serious, unstable medical or psychiatric condition as determined by self-report; 2) Regularly use any form of nicotine or tobacco other than cigarettes (i.e. greater than 9 times per month); or 3) Are pregnant or breast feeding based on self-report (subjects will be given a urine pregnancy test at the screening visit with pregnancy later in the study and breast feeding based on self-report). Regular users of e-cigarettes will be excluded as they likely have identified a preferred flavor.

As the risks associated with the study procedures are small, all medical assessments are based on self-report (except for a urine pregnancy test at screening).

Recruitment will be limited to African American smokers since menthol cigarette use is particularly prevalent in this community³ and because data suggest that greater difficulty in cessation of menthol (vs. non-menthol) cigarettes may be limited to African Americans.³ Regulation of menthol in non-cigarette tobacco products (such as e-cigarettes) may therefore be particularly relevant to this population.

African American menthol smokers will be recruited via the use of flyers and advertisements in local and neighborhood newspapers with a high African American readership or on internet resources such as Craigslist or Facebook. If additional advertisement becomes necessary, radio or television advertisements may be utilized.

Implementation Plan

Overview: Each subject will attend a screening visit to determine eligibility for the study. If subjects are eligible, they will be scheduled to attend a baseline visit until which they will be asked to continue smoking in their normal manner in order to gather information on their baseline smoking patterns. At the baseline visit, subjects will be randomized to either the 'simulated menthol cigarette ban' or 'no menthol cigarette ban' conditions and additionally will be randomized to the order in which they will receive their assigned e-cigarettes (i.e., menthol flavored e-cigarettes followed by non-menthol tobacco flavored e-cigarette or vice versa). Based on their randomization, subjects will be instructed

as to whether they are to abstain from menthol cigarettes and will be provided a supply of e-cigarettes in the flavor they were randomized to for the first 4 week period. Subjects will be seen at visits scheduled approximately two and four weeks after starting use of their assigned e-cigarettes and will receive a phone call one week after starting use of their e-cigarettes to address any questions that arise. At the week four visit, subjects will receive a supply of the alternate e-cigarette products that they will use for the subsequent four week period. We do not believe that a washout period is needed based on a published cross-over study in which differences were found between menthol and tobacco flavored e-cigarettes after each was used for only a 7 to 10 day period (with no wash-out in between).²² During the second four week period, subjects will again receive a phone call 1 week after starting use of their assigned e-cigarette product and will be seen at visits scheduled two and four week after starting use of their assigned product. In order to ascertain if subjects change their tobacco use behavior once e-cigarettes are no longer provided by the study, subjects will have an additional follow-up visit 12 weeks after the baseline visit (i.e., four weeks after the end of the second assessment period). Subjects who complete the entire study will therefore be seen at a screening visit and 6 additional visits over an approximately 3 month period. The procedures occurring during each of these visits are described below.

Vuse brand of e-cigarette (manufactured by RJ Reynolds) were selected for this study for several reasons. Studies suggest that as e-cigarette technology evolves, newer products become more effective at delivering nicotine than older products and are perceived as more satisfying.^{16, 28} Vuse is one of the newest and most commonly used products currently on the marketplace. Vuse was introduced nationally in June 2014 and based on reports from May 2015 has achieved the highest market share of any product at 35.7% of the US market.²⁹ Vuse is available in regular and menthol flavor and is therefore appropriate for this investigation.

Screening Visit: All subjects will complete a screening visit prior to enrollment at which written informed consent will be obtained and eligibility will be verified. Medical and psychiatric history will be obtained via subject report. Baseline questionnaires assessing smoking history will be administered. Exhaled carbon monoxide (CO) will be measured to confirm that they are smokers (CO \geq 8 ppm) with a NicCheck performed (with a cut-off of \geq 5) for those who state that they smoke \geq 5 cigarettes per day but for whom CO is less than 8 ppm (e.g., they didn't smoke that morning, they are coming from a smoke free work environment, etc.). Subjects that qualify and are interested in participating will be asked to maintain a paper smoking diary for the duration of the study and will be scheduled for the baseline visit.

Baseline and Evaluation Visits: Subsequent to the screening visit, there will be a baseline visit and four additional evaluation visits scheduled at approximately 2 week intervals (i.e., at 2, 4, 6 and 8 week after the baseline visit). A follow-up visit will occur at week 12 (i.e., 4 weeks after e-cigarettes are no longer provided to subjects).

To the baseline visit, subjects will bring a first morning urine sample from which baseline urinary cotinine and total NNAL concentrations will be measured. Exhaled CO will be measured from a breath sample. Tobacco use behavior subsequent to the screening visit will be determined as will subjects' level of craving, withdrawal, motivation, self-efficacy to quit smoking, and support for a ban on a variety of menthol containing tobacco products. Subjects will then be told if they have been assigned to the condition in which they are to abstain from menthol cigarettes for the next eight weeks and will be provided (at no cost to them) with a two weeks supply of the product that they have been randomized to receive (i.e., menthol or tobacco flavored e-cigarettes, based on randomization) for the first four week period. Subjects will be instructed in how to properly use the product and will be given all of the packaging that normally accompanies the product. They will be told to use as much or as little of the product as they like. Subjects will also be provided with a tobacco use diary that they are to complete daily in which they are to record the number of cigarettes smoked and how often and how many puffs they used of their provided e-cigarette. Puffs per day has been used in other studies to evaluate e-cigarette use.^{22, 30, 31} They will additionally be asked to record use of any other tobacco or nicotine containing products. Subjects will also be asked to bring to all subsequent visits all e-cigarette cartridges as well as samples of the cigarettes or other tobacco or nicotine products that

they have been using in order to verify the accuracy of the smoking diary. Partially used cartridges will be weighed to determine the extent to which they were used. They will be given no specific instructions regarding using medicinal nicotine (i.e., nicotine patch, gum) or other tobacco products but will be asked to record any instances of using such products.

Evaluation visits will occur at approximately 2 week intervals for eight weeks following the baseline visit. Scheduling considerations will determine the exact intervals of the visits with visits scheduled as close as possible to dates corresponding to those that would occur 2 and 4 weeks after the baseline visit and then 2 and 4 weeks after the week 4 visit (i.e., 2 and 4 weeks after they receive the alternate e-cigarette product). At the week 2 and week 6 visits, subjects will be told that they have 24 points that are worth \$1.00 per point, which they can exchange for cash or additional e-cigarette cartridges of their assigned flavor (at a cost of 3 points per cartridge, which is approximately 66% of the cost of the cartridges commercially). This approach is being used in order to better characterize how menthol vs. tobacco flavored e-cigarettes are likely to be used after subjects have become familiar with the product over the first two weeks. Providing free product for the entire four week period may result in participants using more of the product than they would otherwise use and smoke fewer cigarettes since the e-cigarettes are free and the cigarettes are not. Differences between menthol and non-menthol e-cigarette conditions may therefore be underestimated in this circumstance. Products are offered at a discount to the price available in the retail marketplace in order to ensure that any cartridges are obtained from us (rather than commercially) but to minimize hoarding of the points.

At each visit, exhaled carbon monoxide concentrations will be measured and subjects will complete questionnaires assessing craving and withdrawal symptoms, motivation to quit smoking, product liking, perceived health risks of using the product, and level of support for a ban on a variety of menthol containing tobacco products. The tobacco use diaries that subjects had been asked to complete will be collected at each visit.

At the week 4 and week 8 visits, subjects will be asked to bring a urine sample with their first morning void which will be used to measure urinary cotinine and urinary total NNAL concentrations.

Follow up visit: Subjects will attend one follow-up visit that will occur at week 12 of the study period (i.e., four weeks after they are no longer provided e-cigarettes). To this visit, subjects will again be asked to bring their first morning urine void and an exhaled CO will be measured. The final set of tobacco use diaries will be collected. Questionnaires assessing level of craving, withdrawal, motivation and self-efficacy to quit smoking, perceived health risk, and support for a ban on a variety of menthol tobacco products will be completed as in the evaluation visits. All subjects will be provided information regarding the smoking quitline as a resource available if they are interested in quitting smoking.

As the purpose of this formative proposed project is to provide pilot data for a subsequent grant submission, subjects will be asked at the end of the study ways in which to improve future studies addressing menthol e-cigarettes (for example, asking what they would change about the study and how honest they think others were in their reporting of menthol cigarette use). Subject responses will be examined for consistent themes so as to help inform study design for future projects.

Subjects will be paid \$20 for the screening visit, the baseline visit and each of the 5 subsequent visits (i.e., visits at week 2, 4, 6, 8, and 12). Subjects who complete all scheduled visits and have complied with study related procedures will receive a \$60 bonus. Subject can therefore receive up to \$200 for completing the study in addition to payment for points that were not redeemed for e-cigarette cartridges during the final two weeks of each evaluation period. Subjects will additionally be provided bus tokens (for those who take public transportation) or parking (for those who drive) for each visit.

Data and Safety Monitoring Plan:

In this study, one-half of smokers will be asked to stop using menthol cigarettes and all smokers will be provided e-cigarettes to use over a 2 month period. Those randomized to abstain from smoking menthol cigarettes will be given no specific instructions regarding modifying their smoking

behavior in order to more closely mimic what would occur if menthol cigarettes were banned. Based on our previous research, it is expected that most will smoke non-menthol cigarettes instead.

Risks that subjects are exposed to as a result of enrolling in the study are minimal. Although smoking is clearly detrimental to health, we do not anticipate that their risk will increase as a result of being enrolled in the study since we will only be enrolling those who already smoke at least 5 cigarettes per day. Furthermore, any short term changes in smoking that occur as a result of either being asked to abstain from smoking menthol cigarettes or from using e-cigarettes for an 8 week period are not likely to have long term health effects. The e-cigarettes used for this study are commercially available and among the most commonly used brands. Although these products do not currently undergo regulatory evaluation, they are easily available and increasingly being used. The risks of using e-cigarettes are not thought to be greater than of smoking (with many advocating that these products are less harmful than smoking). E-cigarettes do contain nicotine and it is possible that overuse can lead to symptoms of nicotine toxicity such as nausea, vomiting, dizziness, weakness and rapid heartbeat. The e-cigarette liquid contains propylene glycol which may be associated with throat irritation. The e-cigarette is a battery powered electronic device so malfunctions are possible. As with any product, there is a risk that unanticipated effects from using the e-cigarette may occur. The risk however of using the product is no higher than it would be if subjects were to buy the e-cigarettes themselves and use them outside of the study.

The study procedures will consist of filling out questionnaires, maintaining a tobacco use diary, and providing breath and urine samples. These activities are not expected to pose any risk to subjects. This study will be submitted for approval by the University of Minnesota Institutional Review Board. The study will be explained to all subjects and all subjects will have an opportunity to ask any questions prior to signing an informed consent form. Informed consent will be obtained by one of the investigators or a study coordinator trained per university guidelines. No study related procedures will take place until an informed consent form has been signed. Subjects with serious, unstable medical or psychiatric conditions at the time of screening will be excluded from the study since their pattern of smoking may be influenced by their concurrent disease states.

To ensure confidentiality, all subjects enrolled in the study will be assigned a study identification code which will be used on all study related data collection forms except for those on which the use of personal identifiers is mandatory (e.g., informed consent form). Forms that link the name of the participant and the subject identification code will be kept in a locked cabinet or office or in an electronic file stored on password protected secure computer servers that meet university guidelines. Access to subject identifiable information will be limited to those that require this information such as investigators or others who have direct contact with study subjects (e.g., study coordinator).

At each visit, subjects will be asked if they are experiencing any adverse effects or difficulties with the study. The Principal Investigator will review reports with study staff to determine if changes are needed to any of the study related procedures or if the subject has symptoms/difficulties that would warrant discontinuation from the study.

Data Analysis

The primary aim of the proposed study is to compare changes in each outcome measure (e.g., number of cigarettes smoked, amount of e-cigarette used, motivation to quit smoking, biomarker concentrations, support for a menthol ban) between the four week period when subjects are provided menthol e-cigarettes compared with the four week period when subjects are provided tobacco flavored e-cigarettes. An additional aim is to determine if cigarette type (i.e., randomization to menthol vs non-menthol) moderates the effects of e-cigarette type.

Outcomes will be described using means and standard deviations, separately for each combination of visit and experimental condition (menthol cigarettes available or not, menthol or non-menthol tobacco flavored e-cigarette). Skewed variables will be log transformed and their geometric means and 95% confidence intervals will be reported. Hypothesis testing will be performed using linear mixed models, with fixed effects for randomization group and time, and a random subject effect. The study is designed to provide pilot data to estimate broad trends and parameters that can be used

to plan larger studies. Enrolling a total of 40 subjects with 15-20% attrition would leave at least 16 subjects per group to compare menthol vs. no menthol cigarettes allowed, and those 16 can be compared within each group to test the effects of e-cigarette flavor since all subjects will receive both flavor options in a crossover design. This would result in approximately 80% power to conclude significance at the two sided 0.05 level if the true effect size is 1.0.

The results of this study will be used to plan future projects that would more definitively address the question of how menthol flavoring in e-cigarettes should be regulated. This formative study would inform future research by 1) demonstrating the acceptability of menthol and non-menthol flavored e-cigarette use in this population; 2) providing pilot data regarding how menthol flavoring in e-cigarettes affects (in the presence and absence of a simulated ban on menthol cigarettes) smoking changes, thereby enabling more informed hypotheses to be developed and more accurate sample size calculations to be performed and 3) providing information for study design refinement via the descriptive data collected from participants regarding their recommendations for future study designs.

Data and Record Keeping:

Data will be managed by the study coordinator(s). To ensure confidentiality, all subjects will be assigned a study identification code to be used on all data collection forms except those for which use of personal identifiers is mandatory (e.g., informed consent form). Forms that link the name of the participant and the subject identification code will be kept in a locked cabinet or office or in an electronic file stored on password protected secure computer servers. Access to subject identifiable information will be limited to those that require this information such as study investigators or others who have direct contact with study subjects (e.g., study coordinator).

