Design Overview: This study will enroll approximately 40 African American menthol cigarette smokers who will be randomized to a condition simulating a menthol cigarette ban (i.e., required to abstain from menthol cigarettes for two months) or to a condition in which menthol cigarettes continue to be available (i.e., no restrictions on the cigarettes they can smoke). Within each group, subjects will complete a four week period during which they will be assigned menthol flavored e-cigarettes and a four week period during which they will be assigned regular flavored e-cigarettes. The order in which the e-cigarettes (i.e., menthol vs. regular flavors) will be assigned will be randomized. During each four week period, subjects will be instructed to use their assigned e-cigarettes ad libitum. After completion of the two study periods, subjects will continue to be followed for an additional 4 week period to determine if any changes in tobacco use patterns persist after e-cigarettes are no longer provided to subjects. Tobacco use (e.g., cigarettes, e-cigarettes), other nicotine containing product use (e.g., medicinal nicotine), product liking, motivation to quit smoking, biomarkers of tobacco and toxicant exposure, and support for banning menthol flavoring in tobacco products will be assessed during the study. This project will provide preliminary data regarding how the continued availability of menthol flavored e-cigarettes affects tobacco use behavior in the context of a ban on menthol flavored cigarettes and in the case that menthol flavored cigarettes are not banned. These data will be used to inform the study design and to power a larger study assessing the regulatory implications of the availability of menthol flavored e-cigarettes.

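### In the ban arm the menthol restriction and the e-cigarette supply both end at week 8, so a week 8–12 change there cannot be attributed to loss of e-cigarettes alone

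*Combined protocol and SAP*

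**What the plan says.** **Length of the ban.** The Design Overview describes ban-arm subjects as "required to abstain from menthol cigarettes for two months". The Subjects section makes it an eligibility condition that they "agree to abstain from menthol cigarettes for an 8 week period". At the baseline visit subjects learn whether "they are to abstain from menthol cigarettes for the next eight weeks".

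**Length of the e-cigarette supply.** There are two four-week periods, one per flavour, starting at baseline. The Data and Safety Monitoring Plan confirms that "all smokers will be provided e-cigarettes to use over a 2 month period".

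**Follow-up.** The only later visit is at week 12, which the Follow up visit section places "four weeks after they are no longer provided e-cigarettes". The Design Overview gives its purpose as "to determine if any changes in tobacco use patterns persist after e-cigarettes are no longer provided to subjects". Specific Aims and the Implementation Plan overview express the same purpose, again only in terms of e-cigarettes ending and again for all subjects.

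**Analysis.** The Data Analysis section promises summaries for every visit by ban condition and flavour. For hypothesis tests it gives a linear mixed model with group and time as fixed effects and subject as a random effect. It names neither a group-by-time term nor a week 8 to week 12 contrast.

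No section extends the ban past week 8, says what ban-arm subjects are told about menthol cigarettes in weeks 8–12, or notes that two conditions end together.

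**The concern.** The follow-up month is meant to show what remains once e-cigarettes are withdrawn. In the no-ban arm only the supply changes at week 8. In the ban arm menthol cigarettes become permissible again at the same moment. If smoking rises there between weeks 8 and 12, the reason may be that e-cigarettes have gone, that menthol cigarettes have returned, or both.

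The risk is misattribution. A ban-arm change, or a change common to both arms from the additive model, would be reported under the stated objective as an effect of e-cigarette withdrawal when part of it may come from the end of the ban. The protocol says the data will inform the design of a larger study, so such a reading could be carried forward.

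**Working it through.** **1. The plan's own figure.** The Data Analysis section enrols 40 subjects and allows 15–20% attrition: 40 × 0.80 / 2 = 16 per arm and 40 × 0.85 / 2 = 17 per arm. Power for a standardized effect of 1.0 at two-sided 0.05 with 16 per arm, by the normal approximation, is Φ(1.0 × √(16/2) − 1.96) = Φ(0.868) = 80.7%, which reproduces the stated figure of about 80%. The two-sample t calculation gives 78.1% with 16 per arm and 80.7% with 17. The present point does not depend on this; it supplies only the arm sizes.

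**2. Timeline.**

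| | Baseline to week 8 | Weeks 8–12 | What changes at week 8 |
|---|---|---|---|
| No-ban arm | e-cigarettes supplied, menthol cigarettes allowed | no supply, menthol cigarettes allowed | supply ends |
| Ban arm | e-cigarettes supplied, no menthol cigarettes | no supply, no stated restriction | supply ends and ban ends |

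**3. What can be identified.** Let E₀ and E₁ be the effects of stopping e-cigarettes in the no-ban and ban arms, and B the effect of lifting the ban. The expected week 8–12 changes are:

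- no-ban arm: E₀
- ban arm: E₁ + B

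Within the ban arm, E₁ and B always occur together. The design matrix for weeks 8 and 12 has rank 2 for 3 parameters, so the two cannot be separated.

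With both arms and the assumption E₀ = E₁, the between-arm difference in change equals B, and everything is estimable (rank 4 of 4). If E₀ and E₁ may differ, it is not (rank 4 of 5). The equality assumption sits uneasily with the central hypothesis in Specific Aims, which is that e-cigarette effects depend on whether menthol cigarettes are available.

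**4. What the additive model would report.** With group and time as main effects only and arms of equal size, the single week 8–12 change is the average of the two arms: (E₀ + E₁ + B) / 2. If E₀ = E₁ = E, this is E + B/2. Half of any ban-lifting effect would be read as the effect of stopping e-cigarettes.

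**5. Illustrative size.** The Preliminary data section reports a fall from 11.9 to 9.8 cigarettes/day over four weeks without menthol cigarettes: 11.9 − 9.8 = 2.1, or 2.1 / 11.9 = 17.6%. Taking this as an illustrative upper figure for B:

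| Share of the pilot fall reversed | Shift in ban-arm change (B) | Shift in common change (B/2) |
|---|---|---|
| none | 0 | 0 |
| half | 1.05 | 0.53 |
| all | 2.1 | 1.05 |

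Units are cigarettes/day. The last column applies only if the common change is the one reported.

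**6. Precision.** Basing the withdrawal estimate on one arm instead of two widens its standard error by √(32/16) = 1.41 if the change has the same SD in both arms. A between-arm contrast of week 8–12 change with 16 per arm has 80% power for (1.96 + 0.842) × √(2/16) = 0.99 SD of the change score (1.02 SD by the t calculation), so only a large difference would be detected.

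**The case against.** Several points on the other side are sound.

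- **The arms are already separated descriptively.** The Data Analysis section plans summaries by visit and ban condition, and week 12 is a visit. A reader might infer that the plan pools the arms at week 12. No section proposes that. The gap is narrower: the inferential model names no term that lets the week 8–12 change differ by arm, and nothing says the ban-arm result needs a different interpretation.
- **The follow-up question is descriptive.** The protocol asks whether changes persist and does not explicitly promise to attribute a rebound to one cause. A reader might infer that the ban-arm week-12 visit has no value for persistence. That goes too far: the visit does show whether changes persist after both conditions end. If the return of menthol cigarettes tends to raise smoking, as the pilot's direction suggests, a maintained reduction is evidence of persistence despite it. Only a rebound is ambiguous.
- **The ban-arm data still contribute.** They support a between-arm contrast, subject to the equal-effect assumption.
- **The pilot figure is weak support.** It comes from an open-label, single-group study without study e-cigarettes. Using it as a rebound assumes that the fall was caused by the ban, would apply on top of e-cigarette use, and would reverse within four weeks. The documents establish none of these, and zero is equally compatible with them.
- **No main comparison is affected.** Persistence is in neither Aim 1 nor Aim 2, and the study is a pilot.

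These points limit the claim and its weight. They do not remove the confounding, because the objective is worded for all subjects as a matter of e-cigarettes ending, and the ban is nowhere mentioned as ending with them.

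**Conclusion.** The point holds in a limited form. Both conditions end at week 8 in the ban arm, so a week 8–12 change there cannot be attributed to loss of e-cigarettes rather than to the end of the ban. The additive model as listed would carry this into a common week 8–12 effect.

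The conclusion assumes that the restriction lapses at week 8, as all three statements of its length imply, and that no group-by-time term was intended but left unwritten. The illustrative shift in the ban-arm change is 0 to 2.1 cigarettes/day, resting on the pilot assumptions set out above; it is neither an estimate nor a strict bound. The documents do not support the stronger reading that week 12 is uninformative in the ban arm.

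Severity is minor to moderate: a stated follow-up objective is affected, but neither specific aim is.

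**What to change.** Add to the Data Analysis section:

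1. For week 12, estimate change from baseline and change from week 8 separately by randomized arm, using a group-by-time term. Report no pooled week 8–12 effect.
2. Base the conclusion about e-cigarette withdrawal mainly on the no-ban arm, and say that this is a before–after change within one arm.
3. Label the ban-arm result *after both the ban and the e-cigarette supply ended*. State that a maintained reduction is informative and that a rebound is not attributable to one cause.
4. If a between-arm contrast is used to separate the two withdrawals, state its assumption that stopping e-cigarettes has the same effect in both arms.

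The cost is analysis wording and precision: the withdrawal estimate rests on about 16–17 subjects, with a standard error about 1.41 times that of both arms combined. Visits, procedures and treatment conditions stay as they are.
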